### INTERVENTION:

The RM Band (Resonate Forward LLC) is a small, untethered device that is attached to a soft elastic arm band. Inside the band are small vibration motors that deliver vibration like that of a cell phone on vibration mode. Through the controller inside the small box we can “set” the amplitude and frequency of the vibration. The armband is placed on arm that is more effected by tremor (determined by investigator). If both arms are equally effected, then the participants dominant arm will be used. Once the RMBand is in place, the vibration will be set at the frequency dictated by randomized group assignment. The amplitude duty cycle will be set so that the participant can feel the vibration. If the participant cannot feel the vibration, we will note it and continue with the study. Data collection will follow based on above description.

### DATA ANALYSIS PLAN:

Descriptive statistics will be used to characterize participants: frequencies for categorical variables, mean/standard deviation for normally distributed continuous variables, and median/interquartile range

## Vibration Impact on Tremor

for continuous variables with skewed distributions. Because of the exploratory nature of this pilot intervention study, no adjustment for multiplicity is planned with alpha set at 0.05 for determining significance. The analysis plan for each aim will be discussed separately.

Aim 1: To determine the impact of vibration delivered by the RMBand on parkinsonian tremor pre (baseline), during, and post vibration intervention. It is anticipated that a linear mixed effects model (Brown & Prescott, 2006; Verbeke & Molenberg, 2000; Vonesh & Chinchilli, 1997) will be used to test the group effect (low frequency vs. high frequency) as well as testing the effect each frequency across time (pre, during and post). The general form of the mixed linear model is given by  $y = XB + ZU + e$ , where  $y$  is the observed data vector (e.g., stress),  $X$  is a known design matrix,  $B$  is a vector of unknown fixed effects,  $Z$  is a known design matrix,  $U$  is a vector of unknown random effects, and  $e$  is a vector of unknown random errors. This model will include random effect for participant (represented by  $ZU$  in the equation), and fixed effects for group and time (represented by  $XB$  in the equation). The model is flexible enough to model potential cofactors including demographic or disease descriptors. Modeling assumptions such as normality and homoscedasticity will be checked for each model. In the case of non-normal data, a transformation (such as a log-transformation) will be used to normalize the data. Analyses will be performed using SAS software, specifically PROC MIXED and JMP.

Aim 2: To evaluate the safety and tolerability of the RMBand vibration device applied to the arm of the person with Parkinson's disease tremor. Safety and tolerability of the RMBand will be ascertained by qualitative questions such as: How are you feeling? Do you have any pain? What does the vibration sensation feel like? Is it tolerable? How does the arm band itself feel? Is it comfortable? Are you having any unexpected sensations in your arm or fingers? Anything else you would like to comment on? Answers to these questions will be tabulated by group and across groups.

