## Vibration Impact on Tremor

### STUDY DESIGN:

We will perform a two-group, randomized, longitudinal study exploring the feasibility and impact of the RM Band vibration device on tremor of participants who suffer from Parkinson's disease (PD). This study will be a single session study with participants randomly assigned to one of two dose levels. PD patients will be recruited and randomized into either Group A (low dose) or Group B (high dose). Target enrollment for Group A and B is 15 participants each.

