### SAMPLE ADEQUACY:

The overarching goal of this pilot study is to obtain good estimates of means and variances of the three research measures (MDS UPDRS, Tremor Rating Scale & watch device) at pre, during and post vibration therapy change over time within each of the 2 groups. van Belle (2008) proposed that a minimum of 12 subjects is needed to calculate confidence intervals based on a t-statistic with n-1 degrees of freedom, based on the fact that confidence interval half-width decreases rapidly up to n=12, at which point the decrease is less dramatic. Thus, the proposed sample size of 15 subjects per group should be adequate to estimate means and variances to assess group differences and trends over time.

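### Aim 1 names only a random participant effect and no residual covariance, so standard errors for pre–during and pre–post may be too small or too large

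*Combined protocol and SAP*

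**What the plan says.** DATA ANALYSIS PLAN, Aim 1, anticipates a linear mixed model to test the group effect and the effect of each frequency across pre, during and post. On its structure the plan says "This model will include random effect for participant", together with "fixed effects for group and time". The error term "is a vector of unknown random errors"; nothing is said about its independence, its variance at each time or its correlation over time. The software is "specifically PROC MIXED and JMP".

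Normality and homoscedasticity are to be checked, but the only remedy given is a transformation when data are not normal. On significance, "no adjustment for multiplicity is planned with alpha set at 0.05 for determining significance".

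STUDY DESIGN gives the size: "Target enrollment for Group A and B is 15 participants each". SAMPLE ADEQUACY makes estimation of means and variances at each time within each group the main goal, and rests on the rule that "a minimum of 12 subjects is needed to calculate confidence intervals based on a t-statistic with n-1 degrees of freedom".

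DATA COLLECTION sets the during assessment 5 minutes into a 20-minute vibration period, with the device still on. The post assessment follows switch-off. The repeated assessments are expected to take 15 minutes.

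**The concern.** A RANDOM participant intercept in PROC MIXED, with no REPEATED statement, leaves the residuals independent with one variance. That gives one variance for all three times and one correlation for all three pairs, which is compound symmetry. Every time contrast then gets the same standard error.

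The three occasions differ in kind. During is recorded under the stimulus; pre and post are not. By the plan's timings, during runs up to switch-off (5 + 15 = 20 minutes) and post comes after it, so those two may be more alike than either is to pre. Alternatively, pre and post may be more alike because neither has vibration on. A treatment that suppresses tremor may also change the spread. Any of these can make the pairwise differences unequally variable.

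At stake are the confidence intervals and p-values for pre–during and pre–post, which carry the during-treatment and carry-over questions. Silence also leaves the structure to be chosen after the data are seen.

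**Working it through.** **Inputs.** From the documents: 15 per group, two groups, three times, alpha 0.05. Assumed, because the documents do not give them: two-sided tests, complete data, and all standard deviations (SDs) and correlations.

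**Step 1. The plan's own figure.** The 95% half-width in SD units is t(0.975, n−1)/√n. It is 1.242 at n = 5, 0.715 at n = 10, 0.635 at n = 12 and 0.554 at n = 15. The flattening near 12 is plausible. This rule uses each group's own variance at each time, so it does not depend on the mixed model's covariance structure.

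**Step 2. What the random intercept implies.** With complete balanced data, every time contrast has standard error √(2·MSE/n). MSE estimates half the average variance of the three pairwise differences. The true standard error is √(Var(difference)/n). So

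model SE / true SE = √(average difference variance / this difference's variance).

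The ratio is 1 for every contrast exactly when the difference variances are equal (sphericity). Equal variances and correlations are sufficient for that, but not necessary.

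**Step 3. Worked case.** Take unit variances and correlations of 0.6 (pre–during), 0.6 (pre–post) and 0.9 (during–post).
- Difference variances, 2(1 − r): 0.8, 0.8, 0.2; average 1.8/3 = 0.6.
- Pre–during and pre–post: √(0.6/0.8) = 0.87, so the standard error is 13% too small.
- During–post: √(0.6/0.2) = 1.73, so it is 73% too large.

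**Step 4. False-positive rates.** Each pattern was simulated 20,000 times with no true effect, for contrasts within a group (n = 15, 56 error df) and pooled over groups (n = 30, 58 error df). Ranges cover both.

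| Assumed pattern | Pre–during: SE ratio, rate | Pre–post: SE ratio, rate |
|---|---|---|
| All r = 0.7, equal SDs | 1.00, 4.8–4.9% | 1.00, 4.9–5.0% |
| SDs 1.00, 1.18, 0.89; difference variances all 0.8 | 1.00, 5.1–5.2% | 1.00, 5.1% |
| During–post 0.9, others 0.6 | 0.87, 8.9–9.0% | 0.87, 8.8–9.0% |
| Pre–post 0.9, others 0.6 | 0.87, 8.5–8.9% | 1.73, 0.1% |
| Correlations 0.8, 0.64, 0.8 (AR(1)) | 1.13, 2.8–2.9% | 0.84, 10.0–10.1% |
| SDs 1, 0.7, 1; all r = 0.7 | 1.03, 4.3–4.5% | 0.95, 6.2–6.5% |
| SDs 1, 1.5, 1.2; all r = 0.7 | 0.95, 6.1–6.2% | 1.16, 2.4% |

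With a variance specific to each contrast, the rate was 4.8–5.4% in every pattern.

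**Step 5. Would the planned check catch it?** In the third, fourth and fifth rows the variances are equal at all times, so a homoscedasticity check would pass while rates range from 0.1% to 10.1%. Where variances do differ, the plan states no remedy.

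**Step 6. Group main effect.** This test compares participants' averages over the three times and uses the variance of those averages. With complete balanced data, it does not depend on sphericity.

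**The case against.** A reader might infer that the plan commits itself to compound symmetry and that its standard errors are therefore wrong. The documents do not support that. The covariance of the error term is unstated, the model is only anticipated, and PROC MIXED can fit other structures. No variance or correlation by time is given, so no actual error can be shown. The second row of the table has unequal variances and correlations and still gives nominal rates. These objections stand, and they make the point an omission with a conditional consequence.

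A reader might also infer that all of Aim 1 is affected. It is not: the group main effect is sound with complete data (Step 6).

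A third tempting inference is that a pooled residual variance defeats the pilot's goal of estimating variances. SAMPLE ADEQUACY describes estimates within each group, and these can be tabulated whatever model is fitted. An unstructured covariance common to both groups would not supply them either.

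The headline 9% depends on the assumed correlations. A smaller spread during vibration alone moves the rates little (sixth row), and some patterns make pre–during conservative. That is a fair limit on the size. It does not remove the case for naming a structure: the plain reading of the text is a random intercept, and nothing in the plan guards against unequal correlations.

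**Conclusion.** The plan names a random participant effect and leaves the residual covariance unspecified. If it is fitted with default residuals, pre–during and pre–post borrow an average standard error that may be too small or too large. Across the assumed patterns, false-positive rates for these two contrasts run from 0.1% to 10.1%, and there is no error when the difference variances are equal. The conclusion rests on complete data, two-sided testing and covariance values that the documents do not supply. Severity is modest: the study is an exploratory pilot aimed at estimation, and no confirmatory decision hangs on these tests. The change is still worth making because it is cheap and covers a failure that the planned checks would miss.

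**What to change.** In DATA ANALYSIS PLAN, Aim 1, replace the random participant intercept with an unstructured within-participant covariance over the three times: REPEATED time / TYPE=UN SUBJECT=participant, with Kenward-Roger degrees of freedom. The RANDOM intercept must be removed, because keeping both over-parameterises the model. Prespecify heterogeneous compound symmetry as the fallback if the fit does not converge, noting that it frees the variances but still assumes one correlation. Use the same structure for any fit in JMP.

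Report sample variances by time within each group descriptively, since the model pools them over groups.

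The cost is one sentence and one line of code. There are six covariance parameters (three variances, three covariances) instead of two. Error degrees of freedom per contrast fall from 2 × 14 × 2 = 56 to about 2 × 14 = 28, so the critical t rises from 2.00 to 2.05.

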### DATA COLLECTION:

Data will be collected at baseline (prior to vibration start), during treatment (after 5 minutes of vibration start and with vibration still turned on), and after vibration is stopped to assess the duration of effect. Vibration stimulation will last a total of 20 minutes.

Baseline data includes: (1) demographics (date of birth, sex); (2) disease descriptors (date of Parkinson's diagnosis, medication list, medical history, tremor history, and Movement Disorder Society Unified Parkinson Disease Rating Scale (MDS UPDRS) parts II-IV to assess the total burden of motor PD symptoms as well as their impact on activities of daily living for the prior two weeks; and (3) Tremor Rating Scale.

Estimated time to complete is 30 minutes. Demographics and disease descriptors will be obtained directly from patient, confirmation of diagnosis will be confirmed from medical records.

During treatment and post treatment data collection includes: (1) MDS UPDRS – part III only (motor assessment), and (2) Tremor Rating Scale. The time to complete these two assessments is estimated to be 15 minutes.

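### The Aim 1 model names only group and time as fixed effects, so it cannot estimate change under each frequency, and its group coefficient averages in the pre-vibration baseline

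*Combined protocol and SAP*

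**What the plan says.** The Data Analysis Plan, Aim 1, says the linear mixed model will "test the group effect (low frequency vs. high frequency) as well as testing the effect each frequency across time (pre, during and post". These are two questions: low versus high frequency, and the time course under each frequency.

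The same paragraph then lists the terms. "This model will include random effect for participant", and the fixed part is given as "fixed effects for group and time". The only further terms it mentions are optional demographic or disease cofactors.

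Sample Adequacy makes estimation the purpose of the pilot, including "change over time within each of the 2 groups". Data Collection makes the pre-vibration assessment one of the three outcome times, and says post data are taken "after vibration is stopped to assess the duration of effect".

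**The concern.** The terms listed do not answer the questions posed. A separate time course for each frequency needs a group-by-time interaction, a model per group, or change scores, and the plan names none of these. With main effects only, the model assumes that the two frequencies have the same effect over time, which is what the study sets out to examine.

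The low- versus high-frequency result is affected too. Before vibration starts the randomized groups differ only by chance, yet the group main effect gives that time point the same weight as the two that can carry an effect. The estimate is therefore diluted, and it takes in any chance baseline imbalance.

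If only one frequency works, the analysis would report the same average change for both, and that figure could go into the planning of a later study.

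**Working it through.** **Inputs.** From the documents: 15 per group (Study Design); three times, the first before vibration (Data Collection); the model terms and alpha 0.05 (Data Analysis Plan). The documents give no SD, effect size, correlation or power, so there is no planned figure to reproduce. Assumed for illustration: SD 1 at each time, equal within-person correlation r, time categorical, complete data, two-sided tests, D = 0.5 SD.

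**1. What the named model can estimate.** There are 2 × 3 = 6 group-by-time means. Group plus time has 1 + 1 + 2 = 4 fixed-effect parameters, so the fitted change is forced to be the same in both groups. With group-by-time there are 6 parameters, one per mean.

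Example: low frequency changes by 0, high by 0.5 SD at during and post. The named model gives (0 + 0.5)/2 = 0.25 SD for both groups. With group-by-time the estimates average 0.00 and 0.50.

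**2. What the group coefficient is.** It weights the three group differences by 1/3 each:
- effect at during and post: (0 + D + D)/3 = 2D/3 = 0.33 SD
- effect at during only: (0 + D + 0)/3 = D/3 = 0.17 SD

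Random-intercept fits to simulated data agreed with these weights.

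**3. Precision and power, effect equal at during and post.** With n = 15 per group:
- group coefficient: variance (2/n)(1 + 2r)/3, df 28
- plain change contrast (mean of during and post, minus pre): variance (2/n)[(1 + r)/2 + 1 − 2r], df 28
- baseline-adjusted mean of during and post: variance (2/n)[(1 + r)/2 − r²](1 + 1/26), df 27

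The 95% half-width is t × √variance. For the group coefficient it is multiplied by 1.5 to put it on the scale of D, which is valid only if the effect is equal at both times. At r = 0.5, for example, the group-coefficient variance is (2/15)(2/3) = 0.0889, and 1.5 × 2.048 × √0.0889 = 0.92. Power uses the noncentral t.

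| | r = 0.3 | 0.5 | 0.8 | 0.9 |
|---|---|---|---|---|
| Half-width for D, group coefficient | 0.82 | 0.92 | 1.04 | 1.08 |
| Half-width, plain change | 0.77 | 0.65 | 0.41 | 0.29 |
| Half-width, baseline-adjusted | 0.57 | 0.54 | 0.39 | 0.29 |
| Power, group coefficient | 0.23 | 0.19 | 0.16 | 0.15 |
| Power, plain change | 0.25 | 0.33 | 0.68 | 0.93 |
| Power, baseline-adjusted | 0.41 | 0.45 | 0.72 | 0.93 |

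Simulation with 20,000 runs per setting agreed to within 0.01. Type I error was 0.047 to 0.054 for all tests.

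**4. Effect at during only.** The variance of the during-minus-pre contrast is (2/n) × 2(1 − r), df 28. Baseline-adjusted at during it is (2/n)(1 − r²)(1 + 1/26), df 27.

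| Power | r = 0.3 | 0.5 | 0.8 | 0.9 |
|---|---|---|---|---|
| Group coefficient | 0.09 | 0.08 | 0.08 | 0.07 |
| Plain during minus pre | 0.20 | 0.26 | 0.55 | 0.84 |
| Baseline-adjusted at during | 0.27 | 0.32 | 0.58 | 0.84 |

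**5. Chance baseline imbalance.** The SD of the baseline difference is √(2/15) = 0.37 SD. A baseline difference b moves the group coefficient by b(1 + 2r)/3 on average, so an imbalance of one such SD adds 0.19/0.24/0.32/0.34 SD at r = 0.3/0.5/0.8/0.9.

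**The case against.** The strongest reply is that the interaction was meant. The plan commits to a test of each frequency over time, introduces the model as anticipated, gives only a general matrix form, and may be naming factors rather than excluding their interaction. It also says assumptions will be checked for each model, which could cover one model per group. This is a fair account of the likely intent. But the sentence that lists the model terms omits the interaction, no per-group model is stated, and the mention of several models may only mean one per outcome. Even with the interaction added, the plan would not say which contrast is the low- versus high-frequency comparison.

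A second reply is that the intervals in Sample Adequacy, with n − 1 degrees of freedom, can be computed within each group without the mixed model. They can. However, the plan ties its descriptive statistics to characterizing participants and does not specify such outcome summaries, and Aim 1 assigns the within-frequency test to the model.

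Third, the precision argument depends on an unknown correlation, and power is not a design criterion of this exploratory pilot. This stands in part. The plain change contrast breaks even with the group coefficient at r = 0.25 and is slightly worse below that (at r = 0.2, power 0.23 versus 0.25). Baseline adjustment did better than the plain contrast at every correlation tried (0.41 at r = 0.2), but it is a precision choice. The shared time profile and the 1/3 weights do not depend on r.

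**Conclusion.** The concern holds for the model as written. It cannot provide the change within each frequency that Aim 1 and Sample Adequacy call for, and its group coefficient estimates two thirds of a difference present at during and post, or one third of one present at during only. These results are algebraic. They assume categorical time and complete, balanced data; with missing assessments the weights shift, but baseline still contributes.

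The power, half-width and imbalance figures are illustrations that rest on the assumed SD, effect size and equal correlation. They show that the loss grows with within-person correlation.

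Type I error is preserved and the common time effect remains valid. The fault is a wrong estimand for the two frequency questions, usually with lost precision. In a pilot whose purpose is estimation, this needs to be corrected before analysis.

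**What to change.** In Aim 1, state the fixed effects as group, time (pre, during, post) and group-by-time. This is the part needed to deliver the stated aim. Then specify:

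- pre-to-during and pre-to-post change within each frequency, each with a 95% confidence interval;
- the low- versus high-frequency comparison at during and at post separately, in place of the group main effect;
- adjustment of those comparisons for baseline, either with the baseline score as a covariate or with a common baseline mean for the two groups.

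The cost is analysis-plan wording and two more fixed-effect parameters (4 to 6). No new data are needed.

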### SAMPLE ADEQUACY:

The overarching goal of this pilot study is to obtain good estimates of means and variances of the three research measures (MDS UPDRS, Tremor Rating Scale & watch device) at pre, during and post vibration therapy change over time within each of the 2 groups. van Belle (2008) proposed that a minimum of 12 subjects is needed to calculate confidence intervals based on a t-statistic with n-1 degrees of freedom, based on the fact that confidence interval half-width decreases rapidly up to n=12, at which point the decrease is less dramatic. Thus, the proposed sample size of 15 subjects per group should be adequate to estimate means and variances to assess group differences and trends over time.

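### The pilot's goal is means and variances of each measure, and of its change, within each group; the Aim 1 model as written gives one common change and one pooled variance

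*Combined protocol and SAP*

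**What the plan says.** SAMPLE ADEQUACY states the purpose as estimation: "The overarching goal of this pilot study is to obtain good estimates of means and variances of the three research measures". The measures meant are the watch device, the MDS UPDRS and the Tremor Rating Scale, and the estimates are wanted "at pre, during and post vibration therapy change over time within each of the 2 groups". The size, "Target enrollment for Group A and B is 15 participants each" in STUDY DESIGN, is supported by a rule that "a minimum of 12 subjects is needed to calculate confidence intervals based on a t-statistic with n-1 degrees of freedom".

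The DATA ANALYSIS PLAN is worded differently.

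- *Descriptives.* "Descriptive statistics will be used to characterize participants": mean and SD if a continuous variable is normal, median and IQR if it is skewed. Outcomes during and after vibration, and change scores, are not mentioned.
- *Inference.* "no adjustment for multiplicity is planned with alpha set at 0.05 for determining significance".
- *Aim 1 model.* A linear mixed model, fitted in PROC MIXED, "will be used to test the group effect (low frequency vs. high frequency) as well as testing the effect each frequency across time". The terms named are fixed effects for group and for time and a random effect for participant. No group-by-time term and no residual covariance structure are named.
- *Scale.* "In the case of non-normal data, a transformation (such as a log-transformation) will be used to normalize the data". No back-transformation is described.

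Confidence intervals appear only in the sample-size rationale.

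**The concern.** The stated target is specific to each group: a mean and a variance at each time and for the change, separately for low and high frequency. The stated method is a model whose named terms do not separate change or variance by group, and whose described use is testing. Anyone who follows the analysis section to the letter can complete it without reporting the quantities that the sample-size section calls the purpose of the study.

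The likely user of these results is whoever plans the next study. That person needs the mean and SD of change at each frequency, on the scale of the instrument, with an interval showing how uncertain each is at 15 per group. A common change and a pooled variance could mislead if the two frequencies behave differently, and that difference is what the randomized comparison is there to explore. The interval-width argument for 15 would also never be used in the results.

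**Working it through.** **1. The plan's own figure.** No precision target or power formula is given, so 15 cannot be derived. The premise can be checked. The two-sided 95% half-width for a mean, in SD units, is t(0.975, n−1)/√n:

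| n | half-width (SD) | fall from n−1 |
|---|---|---|
| 5 | 1.242 | 22.0% |
| 10 | 0.715 | 6.9% |
| 12 | 0.635 | 5.4% |
| 15 | 0.554 | 4.1% |
| 20 | 0.468 | 2.9% |

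The rule is consistent with its own reasoning, and 15 exceeds 12.

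**2. What the named terms estimate.** Write the model as y = group + time + participant + error.

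- The baseline-to-during change is the time contrast. Without group-by-time it is the same number in both groups.
- With one participant variance and one error variance, the variance of any paired change is 2 × error variance, again the same in both groups.

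**3. Illustration (all inputs assumed).** 15 per group, three times, participant SD 4; true baseline-to-during changes −2 in one group and −8 in the other; error SDs 2 and 5 (variances 4 and 25). Averages over 100 simulated trials:

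| Model | Change, low-change group | Change, high-change group | Error variance |
|---|---|---|---|
| group + time | −4.9 | −4.9 | 16.8 |
| with group-by-time | −2.0 | −7.9 | 14.6 |
| assumed truth | −2 | −8 | 4 and 25 |

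The interaction repairs the mean changes but not the variances. The true SDs of change are √(2×4) = 2.83 and √(2×25) = 7.07. The interaction model gives √(2×14.6) = 5.40 for both.

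**4. Pooling in general.** With equal group sizes and an SD ratio k between groups (k is assumed), the pooled variance divided by the smaller variance is (1 + k²)/2.

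- k = 1.5: (1 + 2.25)/2 = 1.625 times the smaller variance, and 1.625/2.25 = 0.72 times the larger.
- k = 2: (1 + 4)/2 = 2.5 times the smaller, and 2.5/4 = 0.63 times the larger.
- k = 1: no error.

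**5. Scale, only if data are non-normal.** For a log-normal measure, a back-transformed log mean is the geometric mean. The arithmetic mean is larger by exp(s²/2): 1.05, 1.13, 1.38 and 1.65 for assumed log-scale SDs s of 0.3, 0.5, 0.8 and 1.0.

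**6. What group-specific reporting would give at n = 15.** A 95% half-width of 0.554 SD for a mean or mean change. For an SD, limits of √(14/χ²(0.975, 14)) = 0.732 and √(14/χ²(0.025, 14)) = 1.577 times the estimate. For a variance, 0.536 to 2.487 times the estimate.

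**The case against.** The best defence is that a mixed model is an estimation method. PROC MIXED estimates fixed effects and variance components, and the tests are derived from them. A reader might infer that the pilot would end with nothing but p-values, or that no planned analysis yields a mean or a variance. The documents do not support either inference. Nor do they support the idea that the SD of paired change is lost because the correlation between times is unknown: the model returns a pooled SD of change through its error variance. What it does not return, as written, is that SD for each group.

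Other parts of the defence also carry weight.

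- *Descriptives.* The sentence can be read two ways. If it covers outcomes, normal ones would get a mean and SD, but skewed ones a median and IQR instead. If it covers only participant characteristics, it says nothing about outcomes. On neither reading are paired changes or a split by group stated.
- *Interaction.* The aim of testing each frequency over time suggests that a group-by-time term may be intended. That would recover group-specific mean changes. The pooled variance would remain.
- *Covariance.* The plan does not commit to equal variances; it leaves the structure open and says homoscedasticity will be checked. But it states a remedy only for non-normality, so unequal group variances have no planned handling.
- *Transformation.* It is conditional, and no measure is said to be skewed. For a truly log-normal measure the raw mean and variance can be computed from the log-scale estimates, though the plan does not say this will be done.
- *Intervals.* The sample-size section clearly has t intervals in mind. The gap is that the analysis section never schedules them.

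**Conclusion.** The concern holds in a limited form. The stated goal is group-specific means and variances at each time and of change. The planned model, on its named terms, gives a common change and a pooled variance, is described through tests at 0.05, and leaves the original scale when data are non-normal. This is a method that misses its stated target, and not only an unlisted table, because even with group-by-time added the variances stay pooled unless the plan says otherwise.

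The size depends on facts the documents do not give. If the groups have equal variances and similar changes, little is lost. If the SDs of change differ by a factor of 1.5 to 2, the pooled variance is 1.6 to 2.5 times too large for one group and 0.72 to 0.63 times the true value for the other. The scale problem arises only with non-normal data. No figure in the documents is shown to be wrong, and the point does not dispute 15 per group or the absence of multiplicity adjustment. The plan should be changed, but nothing is irretrievable, since the data needed are already to be collected.

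**What to change.** In the DATA ANALYSIS PLAN, under Aim 1:

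1. For MDS UPDRS Part III, Tremor Rating Scale items 1–14 and each watch measure, report by frequency group and on the original scale: n, mean and SD at pre, during and post; and the mean and SD of the paired changes during-minus-pre and post-minus-pre.
2. Give a 95% t interval (n−1 df) for each mean change and a 95% interval for each SD of change.
3. Show medians with IQR, and any transformed-scale model, beside these and not in place of them.
4. Add group-by-time to the mixed model, so that it matches the stated aim of examining each frequency over time.

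The cost is some wording and one extra table per measure, with no new participants or procedures. The downside is that raw means and SDs are sensitive to outliers, which is the reason to keep the medians alongside.
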